#### 4.3 TREATMENT COMPLIANCE

Treatment compliance is defined as good if between 80-120% of scheduled protocol are received. If the treatment compliance is not between 80-120%, site staff will be reminded about the importance of treatment compliance. However, randomised participants will not be discontinued for poor compliance without prior discussion with the monitor or designee.

Page 74 of 177

[figure not shown]
Proprietary confidential information © 2023 Boehringer Ingelheim International GmbH or one or more of its affiliated companies

# 5. ASSESSMENTS

# 5.1 ASSESSMENT OF EFFICACY

The primary, secondary and further endpoints of the study are specified in Section 2.1.2, Section 2.1.3 and Section 2.2.2, respectively.

Efficacy assessments are primarily based on the reduction of HS lesions count evaluated by the investigator (or appropriately qualified delegate). Adequate identification and counting of draining tunnels, abscesses, and inflammatory nodules are key and require careful training. As much as possible, the same or a reduced number of well-trained evaluators should be assessing lesions at one investigative site to reduce unspecific variability as much as possible.

Efficacy will also be assessed in this study according to patient's reporting outcomes including the assessment of skin pain, pruritus, but also drainage and odour, Dermatology Life Quality Index, HiS-QoL.

The description of specific scores, index, or PROs used as efficacy outcome is provided below.

# Part 1 (Phase IIb) and Part 2 (Phase III)

# 1. International Hidradenitis Suppurativa Severity Score System (IHS4)

The IHS4 is a validated, clinical scoring system for dynamic assessment of HS severity. Determining IHS4 requires counting nodules, abscesses and dT/sinus tracts making it straightforward to apply in clinical trials [R20-3045]. IHS4 will be evaluated at the timepoints mentioned in the Flowchart, and the detail is provided in Appendix 10.4.

# 2. Hidradenitis Suppurativa Clinical Response (HiSCR50)

The HiSCR50 is one of the most well-known and widely used outcome assessment in HS clinical trials. The HiSCR50 is defined as at least a 50% reduction from baseline in the total AN count, [R20-2976]. HiSCR50 will be evaluated at the time-points mentioned in the Flowchart. Appendix 10.3.

[figure not shown]
# 3. Hidradenitis Suppurativa Area and Severity Index (HASI)

The HASI is modelled after the Psoriasis Activity and Severity Index (PASI). Four classic signs of HS-related inflammation (erythema, induration, open ulcer, and dTs) are included. Each variable in HASI is scored on a Likert scale (0-3) for each predetermined body region.

This is converted

Page 75 of 177

Proprietary confidential information © 2023 Boehringer Ingelheim International GmbH or one or more of its affiliated companies

HASI will be evaluated at the time-points mentioned in the Flowchart, and the detail is provided in Appendix 10.5.

# 4. Hidradenitis Suppurativa-Physician Global Assessment (HS-PGA)

This documents the physician's assessment of the patient's HS at a given time-point. It scores patient disease severity (as either clear, minimal, mild, moderate to severe, or very severe) based on abscesses, dT, inflammatory nodule, and non-inflammatory nodule [R20-3046]. HS-PGA will be evaluated at the time-points mentioned in the Flowchart, and the detail is provided in Appendix 10.6.

# 5. Pain Numerical Rating Scale (NRS Pain)

The HS Pain NRS is an endpoint for the assessment of HS-related pain severity for clinical trials with patients with HS. The Patient Global Assessment of HS Pain will be used to assess the worst HS pain. Ratings will range from 0 (no HS pain) to 10 (HS pain as bad as you can imagine). It is a unidimensional measure of pain intensity and can be administered daily with minimal trial participant burden. Recall period is 24 h and response is given by an 11-point scale ranging from 0 to 10; see Appendix 10.7.

# 6. Pruritus Numerical Rating Scale (NRS Pruritus)

The HS Pruritus NRS is an endpoint for the assessment of HS-related pruritus severity for clinical trials with patients with HS. The Patient Global Assessment of HS Pruritus will be used to assess the worst HS pruritus. Ratings will range from 0 (no itch) to 10 (HS worst imaginable itch). It is a unidimensional measure of pruritus intensity and can be administered daily with minimal trial participant burden. Recall period is 24 h and response is given by an 11-point scale ranging from 0 ("no itch") to 10 ("worst imaginable itch"). Trial participants are asked to rate the intensity of their itch using this scale; see Appendix 10.8.

# 7. Dermatology Life Quality Index (DLQI)

The DLQI is a patient-administered, ten-question, quality of life questionnaire that covers six domains including symptoms and feelings, daily activities, leisure, work and school, personal relationships and treatment [R05-2548]. The DLQI has a one-week recall period. Response categories include "not relevant" (score of 0), "not at all" (score of 0), "a little" (score of 1), "a lot" (score of 2) and "very much" (score of 3). Question 7 is a "yes"/"no" question where "yes" is scored as 3, see Appendix 10.9.

The DLQI will be analysed under six headings as shown in Table 5.1: 1 [R05-2548].

c40061625-02 Clinical Trial Protocol Page 76 of 177

Proprietary confidential information © 2023 Boehringer Ingelheim International GmbH or one or more of its affiliated companies

Table 5.1: 1 DLQI

Domain	Question Number	Score
Symptoms and feelings	Questions 1 and 2	Score maximum 6
Daily activities	Questions 3 and 4	Score maximum 6
Leisure	Questions 5 and 6	Score maximum 6
Work and school	Question 7	Score maximum 3
Personal Relationships	Questions 8 and 9	Score maximum 6
Treatment	Question 10	Score maximum 3

# 8. Hidradenitis Suppurativa Quality of Life (HiS-QoL)

The HiS-QoL is a patient-administered, 17-item instrument to measure HS-specific quality of life in clinical trials with a 7-day recall period [R20-3156]. The 17-item HiS-QoL included four symptom items, eight activity-adaptation items, and five psychosocial items.

# 9. Functional Assessment of Chronic Illness Therapy (FACIT-Fatigue)

The FACIT-Fatigue is a 13-item questionnaire [R10-6433], [R07-4311], [R16-0029] that assesses self-reported fatigue and its impact upon daily activities and function. Answers are based on a 5-point Likert scale. Responses of "not at all", "a little", "somewhat", "quite a bit", and "very much" are available for each question and correspond to scores of 0, 1, 2, 3, and 4, respectively (total score range: 0-52).

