# Patient reported outcomes (PROs)

- Achievement of at least 30% reduction from baseline in Numerical rating scale (NRS30) in Patient's Global Assessment of HS pain at each scheduled assessment.
- Absolute change from baseline in Hidradenitis Suppurativa Quality of Life (HiS-QoL) total score at each scheduled assessment.
- Absolute change from baseline in FACIT-Fatigue scale score at each scheduled assessment.
- Absolute change from baseline in Dermatology Life Quality Index (DLQI) score at each scheduled assessment.
- Absolute change from baseline in Patient Global Impression of Change (PGI-C) score over time.
- Absolute change from baseline in Patient Global Impression of Severity (PGI-S) score over time.

Page 44 of 177

Proprietary confidential information © 2023 Boehringer Ingelheim International GmbH or one or more of its affiliated companies

- Change from baseline in Hidradenitis Suppurativa odour and drainage scale (HODS) at each scheduled assessment.
- Change from baseline in NRS Pruritus at each scheduled assessment.
- Change from baseline in Hospital Anxiety and Depression Scale (HADS) at each scheduled assessment.

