#### 7.2.5 Further objective analyses

All further endpoints are specified in Section 2.2.2 and will be considered exploratory in nature.

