#### **10.11 FACIT-FATIGUE**

# **FACIT Fatigue Scale (Version 4)**

Below is a list of statements that other people with your illness have said are important. Please circle or mark one number per line to indicate your response as it applies to the past 7 days.

	applies to the past 7 days.	Not at all	A little bit	Some- what	Quite a bit	Very much
HI7	I feel fatigued	0	1	2	3	4
HI12	I feel weak all over	0	1	2	3	4
Anl	I feel listless ("washed out")	0	1	2	3	4
An2	I feel tired	0	1	2	3	4
An3	I have trouble starting things because  I am tired	0	1	2	3	4
An4	I have trouble finishing things because I am tired	0	1	2	3	4
An5	I have energy	0	1	2	3	4
An7	I am able to do my usual activities	0	1	2	3	4
An8	I need to sleep during the day	0	1	2	3	4
An12	I am too tired to eat	0	1	2	3	4
Anl4	I need help doing my usual activities	0	1	2	3	4
An15	I am frustrated by being too tired to do the things I want to do	0	1	2	3	4
Anl6	I have to limit my social activity because I am tired	0	1	2	3	4

Page 141 of 177 Proprietary confidential information © 2023 Boehringer Ingelheim International GmbH or one or more of its affiliated companies

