4. CHANGES IN THE PLANNED ANALYSIS OF THE STUDY

All analyses stated in the CTP (latest version) will be performed as planned with the following adaptations.

The below further efficacy endpoints have been updated:

- Achievement of HiSCR50 at each scheduled assessment.
 HiSCR50 is defined as at least a 50% reduction from baseline in the total abscess and inflammatory nodule count, with no increase in the abscess or draining fistula count.
- Absolute change from baseline in Patient Global Impression of Change (PGI-C) score over time.

This endpoint will be updated to:

Patient Global Impression of Change (PGI-C) score at each scheduled assessment over time.

• Absolute change from baseline in Patient Global Impression of Severity (PGI-S) score over time.

This endpoint will be updated to:

Date: 07-08-2024, Version 1.0

Patient Global Impression of Severity (PGI-S) score at each scheduled assessment over time.

The below further efficacy endpoints, which were not specified in the CTP version 2.0, have been added:

- Achievement of HiSCR75 at each scheduled assessment.
 HiSCR75 is defined as at least a 75% reduction from baseline in the total abscess and inflammatory nodule count, with no increase in the abscess or draining fistula count.
- Achievement of HiSCR90 at each scheduled assessment.
 HiSCR90 is defined as at least a 90% reduction from baseline in the total abscess and inflammatory nodule count, with no increase in the abscess or draining fistula count.
- Achievement of mHiSCR at each scheduled assessment: mHiSCR is defined as at least a 50% reduction in total ANdT count relative to baseline. and at least 50% reduction in total dT count relative to baseline.
- Achievement of mHiSCR-AdT at each scheduled assessment: mHiSCR-AdT is defined as at least a 50% reduction in the total AdT count with no increase in inflammatory nodule count, no increase in abscess count, and no increase in dT count relative to baseline.
- Achievement of mHiSCR-AdT(2) at each scheduled assessment: mHiSCR-AdT (2) is defined as at least 50% reduction in the total ANdT count relative to baseline and at least 50% reduction in total AdT count relative to baseline.

Boehringer Ingelheim TRIAL STATISTICAL ANALYSIS PLAN 1368-0098

Date: 07-08-2024, Version 1.0

Page 10 of 64

c43421787-01

- Achievement of 2 points reduction in Physician's Global Assessment (PGA) score from baseline at each scheduled assessment (only for patients with a PGA \geq 2 at baseline).

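### Protocol Section 5.1 scores all 13 FACIT-Fatigue items in one direction although two are worded the opposite way, and no legible text states a reversal or which direction of the total is better

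*Protocol*

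**What the plan says.** Protocol Section 5.1, entry 9, introduces the instrument: "The FACIT-Fatigue is a 13-item questionnaire". It then gives one scoring rule for every question: the five answers, from the lowest to the highest degree of agreement, "correspond to scores of 0, 1, 2, 3, and 4, respectively (total score range: 0-52". It does not say that any item is reversed or which end of the total is favourable.

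Appendix 10.11 reproduces the form. Every item carries the codes 0 to 4 in the same order. Eleven items describe fatigue or its effects (HI7, HI12, An1 to An4, An8, An12, An14 to An16), for example "I feel fatigued". Two describe the opposite state: An5 on having energy, and An7, "I am able to do my usual activities".

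The score enters the analysis through a further endpoint in Protocol Section 2.2.2, "Absolute change from baseline in FACIT-Fatigue scale score at each scheduled assessment", which is listed for Part 1 and again for Part 2. Section 7.2.5 says that all further endpoints "will be considered exploratory in nature".

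SAP Section 4 lists departures from the protocol under the words "The below further efficacy endpoints have been updated" and then adds new endpoints. It revises PGI-C and PGI-S and adds pain-scale endpoints, but FACIT-Fatigue is not among them. In the legible SAP text, FACIT appears only in the list of abbreviations.

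**The concern.** On eleven items a high code means more fatigue. On An5 and An7 a high code means less. A rule that gives every item the same direction and then sums them makes improvement on those two items cancel part of the improvement on the others. Such a total does not measure one thing on one scale. Its raw points are compressed, and they cannot be compared with data in which the items were aligned first.

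The missing direction is a second gap. Under the written rule a fall in the total is mostly improvement. If the eleven items were reversed instead, a rise would be improvement. The protocol text alone does not tell a reader how to interpret the sign of a change from baseline.

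The same protocol closes both gaps for other scales. The HODS entry in Section 5.1 says which direction is worse. The HADS form in Appendix 10.15 prints codes that are already aligned across oppositely worded items. FACIT-Fatigue has neither safeguard.

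**Working it through.** **Inputs.** 13 items, each coded 0 to 4, and a total of 0 to 52 (Protocol Section 5.1). By wording, 11 items describe fatigue and 2 its absence (Appendix 10.11).

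**1. The plan's own figure.** 13 × 4 = 52, so the stated range reproduces. It is the same whether or not items are reversed, so it does not show which rule is intended.

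**2. Consistent extremes under the literal rule.**
- Worst fatigue on every item: 11 × 4 + 2 × 0 = 44.
- No fatigue on any item: 11 × 0 + 2 × 4 = 8.
- Span: 44 − 8 = 36, against 52 with aligned items. Shortfall: 1 − 36/52 = 30.8%.

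A total of 52 would need the highest agreement both with being fatigued and with having energy. A total of 0 would need the denial of both.

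**3. Raw change.** Let each of the 11 items improve by d, and each of the 2 by c × d in its own favourable direction.
- Aligned change: (11 + 2c)d.
- Literal change: (11 − 2c)d.
- Understatement: 1 − (11 − 2c)/(11 + 2c) = 4c/(11 + 2c).

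| c | aligned | literal | understated |
|---|---|---|---|
| 0 | 11 | 11 | 0% |
| 0.5 | 12 | 10 | 16.7% |
| 1 | 13 | 9 | 30.8% |
| 1.5 | 14 | 8 | 42.9% |

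**4. Standardised change.** The documents give no item-level variances or correlations. Assume equal item variances of 1, equal shifts on all items, and a common correlation ρ between aligned items.
- Aligned variance: 13 + 13 × 12 × ρ = 13 + 156ρ.
- Literal variance: 13 + (9² − 13)ρ = 13 + 68ρ, where 9 = 11 − 2.
- Ratio of raw changes: 9/13 = 0.692.

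| ρ | SD ratio (literal/aligned) | standardised effect ratio | loss |
|---|---|---|---|
| 0.3 | √(33.4/59.8) = 0.747 | 0.926 | 7.4% |
| 0.5 | √(47/91) = 0.719 | 0.963 | 3.7% |
| 0.7 | √(60.6/122.2) = 0.704 | 0.983 | 1.7% |

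The SD shrinks almost as much as the change. Under these assumptions the loss in standardised effect is about 2% to 7%.

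**The case against.** Section 5.1 matches the codes printed on the form and gives a range that is correct under either rule. It does not say that the total is the unadjusted sum of those codes. It cites three sources for the instrument, which cannot be consulted here and may contain the scoring rule. Protocol Section 2.2.2 says that details of further endpoints may be defined in the SAP. The SAP refers to Sections 5.4.1, 5.4.2 and 10.3, none of which is visible in this copy, and the endpoint pages after Section 5.2.2 are blank. SAP Section 4 lists only changes from the protocol, so its silence on FACIT-Fatigue does not show that no derivation exists. The endpoint is exploratory, and because responses are recorded item by item, the total can be recomputed at any time.

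Most of this stands. A reader might infer that FACIT-Fatigue will be scored wrongly and that its change will be understated by 31%. The documents do not support that: the derivation is not visible, and 30.8% applies only to the full span or to equal movement on all items. A reader might also infer a 31% loss of sensitivity. That does not follow either, because the SD shrinks with the change.

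One part does not stand. Section 5.1 goes beyond naming the instrument: it assigns scores to the answers for every question and gives a total. That mapping does not fit the items in Appendix 10.11. If the SAP or a cited source holds a reversal rule, Section 5.1 omits it and still needs correcting.

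**Conclusion.** The point holds as a defect in the protocol's scoring text. Applied as written, the rule sums items that run in opposite directions, and no legible text supplies a reversal or a direction. The size is conditional on literal summation: a usable span of 36 of 52 points, and raw change understated by 30.8% with equal item movement, or by 0% to 43% for c between 0 and 1.5. The 2% to 7% loss on the standardised scale rests on assumed correlations of 0.3 to 0.7.

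The consequence is limited to the interpretation of an exploratory endpoint in raw points, its comparison with aligned data, and the meaning of its sign. The Part 1 primary and secondary efficacy endpoints concern dT count and IHS4 and are unaffected. It would also go too far to say which alignment is right. Reversing the two items or the eleven removes the conflict equally well, and neither document chooses.

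**What to change.** In Protocol Section 5.1, state which items are reverse-scored before summation so that all 13 point the same way, and state whether a higher total means more or less fatigue. Confirm both against the scoring source that the protocol cites. Check that the SAP derivation says the same, and add it if it is absent.

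The cost is a sentence or two in the protocol and a check of the SAP derivation. The questionnaire and its collection do not change, and item responses already recorded can be scored under the corrected rule.

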# 10. Patient Global Impression of Change (PGI-C)

The PGI-C is a 1-item tool assessing the change of HS by start of taking the study medication by 5-point Likert-type scale. The first assessment of PGI-C is performed at Visit 6 and after that, as indicated in the Flowchart. The tool is required for anchoring of other instruments and endpoints, see Appendix 10.12.

Boehringer Ingelheim BI Trial No.: 1368-0098

c40061625-02 Clinical Trial Protocol Page 77 of 177

Proprietary confidential information © 2023 Boehringer Ingelheim International GmbH or one or more of its affiliated companies

# 11. Patient Global Impression of Severity (PGI-S)

The PGI-S is a 1-item tool assessing the severity of HS over the last week by 4-point Likert-type Scale. The first assessment of PGI-S is performed at Visit 2 tool is required for anchoring of other instruments and endpoints; see Appendix 10.13.

# 12. Hidradenitis Suppurativa odour and drainage scale (HODS)

The HODS is an 8-item scale developed to assess the HS-related drainage and odour in patients. It covers two domains: drainage (5 items) and odour (3 items). The response options range from 1-5. Higher scores depict worse outcome of the concept being assessed; see Appendix 10.14.

# 13. Hospital Anxiety and Depression Scale (HADS)

The HADS is an instrument for screening anxiety and depression in non-psychiatric populations. The HADS consists of 14 items, 7 each for anxiety and depression symptoms; possible scores range from 0 to 21 for each subscale; see Appendix 10.15.

# Part 2 (Phase III) only

14. Work Productivity and Activity Impairment Questionnaire for HS (WPAI-HS) WPAI-HS is 6-item instrument to assess the effect of hidradenitis suppurativa on ability to work and perform normal daily activities; see Appendix 10.16.

# 15. EuroQol 5 dimensions 5-level (EQ-5D-5L)

Assessment of changes in quality of life using the EuroQol-5D-5L. The descriptive system comprises five dimensions: mobility, self-care, usual activities, pain/discomfort, and anxiety/depression. Each dimension has 5 levels: no problems, slight problems, moderate problems, severe problems, and extreme problems. The EQ VAS records the patient's self-rated health on a vertical visual analogue scale, where the endpoints are labelled 'The best health you can imagine' and 'The worst health you can imagine'; see Appendix 10.17.

The Patient Global Assessment of HS Pain and HS Pruritus will be completed on a diary (one scale for pain and another for pruritus), on a daily basis by trial participants from Visit 2 through Visit 19 After Visit 19, NRS pain and NRS pruritus will be collected on a daily basis during the 7 days prior to the next scheduled visit as per Flowchart. For details, refer to the Flowchart.

For the daily assessments, trial participants should be instructed that, before they go to bed, they complete the assessment based on a recall period of the "last 24 hours" and respond to the items. This training should be documented in trial participant clinical records.

Further instructions on diary completion can be found in the ISF.

Page 78 of 177

Proprietary confidential information © 2023 Boehringer Ingelheim International GmbH or one or more of its affiliated companies

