- Infection testing: at screening and at EoT visit. See Section of safety laboratory parameters for complete list of testing required (see Table 5.2.3: 2). For Japan only, if there is no chest X-ray test or CT taken within 3 months prior to Visit 1, it should be taken at screening visit. For South Africa only, tuberculosis infection testing should be done approximately at 6 months intervals. For this reason, participants from South Africa QuantiFERON testing should be done at visit 19.
- ECG measurements should always precede blood sampling and drug administration. The ECG measurements need to be conducted at timepoints indicated in the Flowchart. Additional ECG measurements may be performed if the investigator deems it clinically indicated.
- Trial participants who terminate study drug early should do the EoT visit as soon as possible. These participants will then do EoS visits, after last study drug administration. When this discontinuation happens before Visit 14 participants ideally should also continue visits for assessments of efficacy until as per Flowchart.
- Desoxyribonucleic Acid (DNA) banking sample is optional. This sampling is only possible if the trial participant agreed by signing a separate informed consent. For details, please see Section 5.5.
- Skin biopsy is mandatory at selected sites and should be sampled under ultrasound (US) guidance. For all other sites it is optional. Sites without the US required capabilities cannot perform skin biopsies. See Section 5.4.4.
- 13 US lesion evaluation is mandatory at selected sites with US capabilities. For all other sites it is optional. See Section 5.4.3.
- 14 IHS4 is used to classify trial participant's severity at baseline. IHS4 will be derived from lesions count by a trained health care professional
- Trial participant diaries will be handed to trial participants with the objective to collect daily information about NRS Pain and Pruritus from baseline, after being trained, till Visit 19 After Visit 19, NRS pain and NRS pruritus will be collected on a daily basis during the 7 days prior to the next scheduled visit (prior to Visit 23, Visit 27, Visit 31, and EoT visit). Site staff will collect the diaries from trial participants at visits indicated in the Flowchart to assess pain and pruritus since last visit. See Section 5.1.1.
- 16 At Screening, the C-SSRS baseline/screening scale will be completed. At all subsequent visits the "since last visit" scale will be completed.

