#### **Clinical Trial Protocol**

Page 16 of 177

- 17a At Visit 2, instructions for paper version of patient's daily diary will be dispensed to trial participants. Site staff should provide adequate training. Two weekly diaries and one additional
- Once electronic diary is available instructions for electronic diary will be dispensed to trial participants. Site staff should provide adequate training. Trial participant diary captures until Visit 19. From Visit 23, trial participants will record data for pain and pruritus during the last 7 days before the applicable visits (one daily diary on the last 7 days before the next scheduled visit). Analgesic use and other interventions to manage pain will be collected at the same time points, but in paper format.
- 18 Trial participant's diaries returned by participants must be reviewed while the trial participant is in the consultation, so that any information can be clarified in an interview with the trial participant, if needed.
- For local tolerability at the administration site of the IMP, the investigator will perform an assessment during the study drug administration visit and at the time of AE assessment by questioning retrospectively since the last visit. Any observed local tolerability reaction, e.g. "swelling", "induration", "heat", "redness" should be evaluated and reported as adverse events.
- 20 All trial participants completing of the trial may be
- 21 For South Africa only, tuberculosis infection testing should be done approximately at 6 months intervals. For this reason, participants from South Africa

c40061625-02 Clinical Trial Protocol

Page 17 of 177

Proprietary confidential information © 2023 Boehringer Ingelheim International GmbH or one or more of its affiliated companies

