#### Part 2 (Phase III)

# **Efficacy**

Key secondary endpoints

The following key secondary endpoints will be considered. These may be amended according to Part 1 results:

- Absolute change from baseline in IHS4 value at
- Absolute change from baseline in Hidradenitis Suppurativa Area Severity Index (HASI) score at
- Achievement of Hidradenitis Suppurativa Clinical Response (HiSCR50) at Week 16: HiSCR50 is defined as at least a 50% reduction in the total abscess and inflammatory nodule (AN) count with no increase in abscess count and no increase in dT count relative to baseline.
- Percent change from baseline in abscess count at
- Achievement of at least a 50% reduction in dT count at relative to baseline.
- Achievement of at least a 50% reduction in abscess and dT (AdT) count at relative to baseline
- Achievement of at least a 50% reduction in ANdT count at relative to baseline.
- Achievement of at least 30% reduction from baseline in Numerical rating Scale (NRS30) in Patient's Global Assessment of HS pain at

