- Achievement of at least 30% reduction from Week 1 measurement in Numerical rating scale in Patient's Global Assessment of HS pain at each scheduled assessment.
- Percent change from baseline in Numerical rating scale in Patient's Global Assessment of HS pain at each scheduled assessment
- Percent change from Week 1 in Numerical rating scale in Patient's Global Assessment of HS pain at each scheduled assessment

Proprietary confidential information © 2024 Boehringer Ingelheim International GmbH or one or more of its affiliated companies.

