6.7 BASELINE, TIME WINDOWS AND CALCULATED VISITS

Unless otherwise specified, measurements reported with date and time and taken prior to start of administration of trial treatment will be considered pre-treatment values; measurements reported with a date only (and no time) and taken on the day of first administration of trial treatment will also be considered pre-treatment values. These pre-treatment values will be assigned to visits according to the nominal visit number as recorded on the eCRF or as provided by the laboratory.

Patient reported output (PRO) measurements reported prior to/on the date of the drug administration will be taken as pre-treatment values, regardless the time of measurements taken if there exist.

Baseline, unless otherwise specified, is defined as the last measurement collected prior to the start of administration of the trial treatment.

Measurements taken after start of administration of trial treatment will be considered either on- or off-treatment values based on the definition in Section 6.1, and will be assigned to visits for statistical analysis, if applicable, as defined below.

[figure not shown]
Analysis of AE data, potentially clinically significant abnormal laboratory values, concomitant medication or non-drug therapies, as well as use of rescue medication will not be based on visits. Frequency tables for these data will be using on-treatment data and categorized based on their occurring/starting dates. Therefore, no assignment to time windows will be necessary for such data.

The derivation of the last value, minimum value and maximum value of laboratory and vital signs data will consider all on-treatment values (whether or not selected in any time window; see Table 6.1: 1 for definition of the on-treatment period) within the period of interest; these will be derived for analysis of laboratory and vital signs data.

All other safety, efficacy and biomarker measurements will be assigned to visits based on extended time windows around the planned visit dates, defined relative to the day of first trial treatment (which is scheduled for Visit 2). These extended time windows are defined in Table 6.7: 1 and Table 6.7: 2.

c43421787-01

c43421787-01

c43421787-01

Proprietary confidential information © 2024 Boehringer Ingelheim International GmbH or one or more of its affiliated companies.

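### No pain-diary run-in is described: on a one-day Visit 2 the only diary baseline for NRS30 is a single bedtime entry made after the first dose

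*Protocol*

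**What the plan says.** - **When the diary starts.** Protocol Section 5.1 has the pain and pruritus scales completed "on a daily basis by trial participants from Visit 2 through Visit 19". A flowchart footnote agrees: data are collected "from baseline, after being trained, till Visit 19". Footnote 17a says "At Visit 2, instructions for paper version of patient's daily diary will be dispensed to trial participants". Another footnote identifies Visit 2 as the day of randomisation and first drug intake. Screening may last up to 28 days, and no diary collection is described for it.
- **When in the day.** Section 5.1 tells participants that "before they go to bed, they complete the assessment", with a 24-hour recall.
- **How baseline is picked.** SAP 6.7 defines baseline, unless otherwise specified, as the last measurement before the start of administration. It also states: "Patient reported output (PRO) measurements reported prior to/on the date of the drug administration will be taken as pre-treatment values", whatever the time of the measurement.
- **Where the endpoint sits.** NRS30 from baseline is a further endpoint in Part 1 (protocol Section 2.2.2). It is a potential key secondary endpoint in Part 2 (Section 2.1.3), where the list may change after the Part 1 results.
- **A second reference.** SAP Section 4 adds pain endpoints measured against Week 1, such as "Percent change from Week 1 in Numerical rating scale", and keeps the baseline-referenced ones.

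**The concern.** NRS30 is a ratio against baseline, so error in the baseline goes straight into the response. A single daily score carries the full day-to-day variation. A patient whose one baseline day happens to be bad can meet the 30% criterion with no true change. This occurs in every arm, raises the placebo rate and shrinks the difference between arms.

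The timing adds a smaller problem. If the entry is made after the first dose, part of its recall window is on treatment, so it is not strictly a baseline.

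At stake is the sensitivity of a pain endpoint that may enter the Part 2 key secondary set. Pre-dose diary scores that were never collected cannot be recovered later.

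**Working it through.** The visible text gives no sample size, power or expected rate for NRS30, so there is no plan figure to reproduce. The check has three steps.

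**1. Entries available as baseline.** Assume a dose at 10:00 and a bedtime entry at 22:00. Count the entries strictly before the dose, and those dated on or before the dosing day (the SAP 6.7 PRO rule).

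| Diary handed out | Strictly pre-dose | Under the SAP date rule |
|---|---|---|
| Same day as dose (one-day Visit 2) | 0 | 1 |
| One day before (split Visit 2, Section 6.2.2) | 1 | 2 |
| Two days before (if the flowchart's 2-day window covers the diary) | 2 | 3 |

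In each row the latest entry under the date rule is the dosing-day bedtime entry, 22 − 10 = 12 hours after the dose. Taking the last value under that rule therefore selects one score and, where that evening's entry exists, a post-dose one. Even the widest allowance gives two pre-dose evenings.

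**2. Share of the recall window after dosing.** Share = (22 − dose hour) / 24.
- Dose at 08:00: 14/24 = 58%.
- Dose at 16:00: 6/24 = 25%.

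**3. Effect of a one-day baseline on NRS30.** This is a simulation of 400,000 patients with integer scores from 0 to 10. Follow-up is a 7-day mean, and response means follow-up at or below 0.7 × baseline. None of the inputs comes from the documents.

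*No true change, every patient's mean 5, independent days. Chance responders:*

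| Day-to-day SD | One-day baseline | 7-day mean baseline |
|---|---|---|
| 1.0 | 3.7% | 0.1% |
| 1.5 | 11.1% | 1.7% |
| 2.0 | 17.8% | 5.3% |

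If patient means vary instead (mean 5 or 6, SD 1.8), the ranges over the same day SDs are 3% to 19% with one day and 1% to 7% with seven.

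*True 30% reduction on active, patient means 5 (SD 2), day SD 1.5, independent days:*
- One-day baseline: 49.0% − 12.7% = 36.3 points.
- 7-day baseline: 48.5% − 4.5% = 44.0 points.
- Loss: 44.0 − 36.3 = 7.7 points. Leaving out patients who score zero on the baseline day gives 37 against 44, a loss of about 7.

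*Same inputs, relaxing the assumptions:*

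| Assumption changed | One-day | 7-day | Loss (points) |
|---|---|---|---|
| Day-to-day correlation 0.5 | 35 | 39 | about 4 |
| Day-to-day correlation 0.8 | 32 | 34 | about 2 |
| Single-day follow-up, independent days | 29 | 32 | about 3 |

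The correlation here decays from one day to the next. At 0.8, with no true change and mean 5, chance responders are 18% against 15%: averaging seven highly correlated days removes little noise.

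**The case against.** The strongest case on the other side has four parts.

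**The baseline is not always post-dose.** A reader might infer that it is. Section 6.2.2 lets Visit 2 be split, with diaries handed out on the first day and drug given on the second. A flowchart footnote lets some Visit 2 assessments be done up to 2 days early after consulting the sponsor. Section 6 lets questionnaires be filled in within 24 hours before a visit, without saying whether that covers the pain NRS. Section 6.1 places diaries ahead of dosing in the visit sequence. This stands, and it limits the post-dose statement to a one-day Visit 2. These are allowances, though, not a run-in.

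**Decisive text may be missing.** The flowchart rows, part of footnote 17a, the SAP endpoint derivations and the SAP 6.7 window tables are not in the public version, and the site file holds further diary instructions. SAP 6.7 allows for definitions given elsewhere. So a clinic rating before dosing, or an averaged baseline, cannot be excluded, and one cannot say that screening collects no pain data. This stands too. The PRO rule may also be meant as an exception to the general rule, but it would still admit a post-dose value.

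**The size is assumed.** No document gives a mean pain score, a day-to-day SD, a correlation or an effect on pain, and the visible text does not state a 7-day follow-up mean. This stands, so the result is a range.

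**Week 1 does not replace baseline.** A reader might infer that the SAP has made Week 1 the baseline. It has not: those endpoints are exploratory additions. Dropping them would be a preference.

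**Conclusion.** The point holds in limited form. As the public text reads, there is no diary run-in and no averaged pre-dose baseline. On a one-day Visit 2 the NRS30 diary baseline is one bedtime score given after the first dose, and the two baseline statements in SAP 6.7 do not agree on whether it qualifies.

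The direction of the effect is clear: more chance responders in all arms and a smaller contrast. Its size depends on how strongly pain scores on neighbouring days are correlated. With the assumed inputs the loss is about 7 to 8 points for independent days and about 2 points at correlation 0.8.

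The documents do not support reading this as a bias in favour of active treatment or as a threat to the Part 1 primary analysis. The noise acts in every arm, and NRS30 is outside the Part 1 primary and secondary endpoints. It is an inexpensive improvement to a potential Part 2 key secondary endpoint. Section 6 already defers the Part 2 investigational plan to an amendment, so the change can be made there.

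**What to change.** 1. **SAP 6.7 (Part 1).** State the NRS baseline explicitly and reconcile the two rules. An NRS entry made after dosing on Day 1 should not count as baseline where a pre-dose entry exists. Where none exists, report how many patients rely on a post-dose entry.
2. **Part 2 amendment.** Dispense the diary and train participants at Visit 1. Define NRS baseline as the mean of the available daily scores in the 7 days before first dose, with a stated minimum, for example 4 of 7. This mirrors the 7 daily scores that the protocol already collects before scheduled visits after Visit 19.
3. **Week 1 endpoints.** They may stay as exploratory summaries. They should not carry between-arm claims, because Week 1 is on treatment and any early effect is absorbed into the reference.

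**Cost:** training moves to Visit 1, and each Part 2 participant makes about one extra week of diary entries. No visit is added. The SAP change is wording only.
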